#### Safety Analysis

All primary safety endpoints and other observed adverse events will be documented and reported. Adverse events will be summarized by the incidence of events by type and by percentage of subjects with those events. Primary safety endpoints that are adjudicated by the Clinical Events Committee (CEC) will be further described by the relatedness to the trial treatment and severity level.

#### Efficacy Analysis

Descriptive statistics will be used to summarize changes from baseline in the PUL 1.2 scores (including the mid-level dimension, combined mid and distal-level dimensions, and high-level dimension), in left ventricular structure and function parameters (including ejection fraction, wall thickness, end-diastolic and end-systolic volumes, stroke volume, and circumferential strain, in pulmonary function (including SVC, FEV1, FVC, MIP, MEP, PCF, and IFR) and in 6-minute walk test distance for ambulatory patients.

# **LIST OF FIGURES**

# 4. LIST OF ABBREVIATIONS AND DEFINITIONS OF TERMS

The following abbreviations and specialist terms are used in this trial protocol.

Term Explanation		
6MWT	Six-Minute Walk Test	
AE	Adverse Event	
ALT	Alanine Aminotransferase	
AST	Aspartate Aminotransferase	
BUN	Blood Urea Nitrogen	
С	Celsius	
CBC	Complete Blood Count	
CDC	Cardiosphere-Derived Cells	
CEC	Clinical Events Committee	
CFR	Code of Federal Regulations	
CK-MB	Creatine kinase MB Isoenzyme	
CLIA	Clinical Laboratory Improvement Amendments	
CRF	Case Report Form	
CRO	Clinical Research Organization	
СТ	Computerized Tomography	
DCM	Dilated Cardiomyopathy	
DMD	Duchenne Muscular Dystrophy	
DMSO	Dimethyl Sulfoxide	
DSA	Donor-Specific Antibody	
DSMB	Data Safety Monitoring Board	
ECG	Electrocardiogram	
EDC	Electronic Data Capture	

### Table 2:Abbreviations and Specialist Terms

Term	Explanation
ESR	Expedited Safety Report
ET	Early Termination
ETFE	Ethylene Tetrafluoroethylene
FDA	U.S. Food and Drug Administration
FEV1	Forced Expiratory Volume in 1 Second
FVC	Force Vital Capacity
GCP	Good Clinical Practice
GMP	Good Manufacturing Practice
HED	Human Equivalent Dose
HEENT	Head, Eyes, Ears, Nose, and Throat
HFrEF	Heart Failure with Reduced Ejection Fraction
HIPAA	Health Insurance Portability and Accountability Act
HLA	Human Leukocyte Antigen
HSA	Human Serum Albumin
IB	Investigator's Brochure
ICH	International Conference of Harmonisation
IFR	Inspiratory Flow Reserve
IND	Investigational New Drug Application
IP	Investigational Product
IRB	Institutional Review Board
ITT	Intent-to-Treat
IV	Intravenous

Term	Explanation
IWRS	Interactive Web Response System
LV	Left Ventricle / Left Ventricular
LVEDV	Left Ventricular End- Diastolic Volume
LVEF	Left Ventricular Ejection Fraction
LVESV	Left Ventricular End-Systolic Volume
М	Million
MACE	Major Adverse Cardiac Event
MCB	Master Cell Bank
MedDRA	Medical Dictionary for Regulatory Activities
MEP	Mean Expiratory Pressure
MFI	Mean Fluorescence Intensity
МНС	Major Histocompatibility Complex
MI	Myocardial Infarction
MIP	Mean Inspiratory Pressure
mITT	Modified Intent-to-Treat
mL	Milliliter
МОР	Manual of Procedures
MRI	Magnetic Resonance Image
MSC	Mesenchymal Stem Cells
OAE	Other Adverse Events
OLE	Open Label Extension
PCF	Peak Cough Flow
PE	Physical Exam
PEF	Peak Expiratory Flow
PFT	Pulmonary Function Test

Term	Explanation					
PI	Principal Investigator					
РР	Per Protocol					
РТ	Preferred Term					
PUL	Performance of the Upper Limb					
QOL	Quality of Life					
RBC	Red Blood Cell					
RV	Residual Volume					
SAE	Serious Adverse Event					
SD	Standard Deviation					
SOC	System Organ Class					
SpO2	Peripheral Capillary Hemoglobin Oxygen Saturation					
SVC	Slow Vital Capacity					
TEAE	Treatment-Emergent Adverse Events					
Term	Explanation					
TIMI	Thrombolysis in Myocardial Infarction					
TLC	Total Lung Capacity					
v/v	Volume to Volume					
WBC	White Blood Cell					
WHO-DD	World Health Organization Drug Dictionary					

# 5. INTRODUCTION

### 5.1. Background

Duchenne muscular dystrophy (DMD) is a severe, X-linked, progressive disease affecting approximately one in 3,600 to 9,200 male births (Mah et al., 2014). It is caused by mutations in the dystrophin gene resulting in the absence of or non-functional dystrophin protein (Hoffman et al., 1988).

Dystrophin is a cytoplasmic protein encoded by the *dmd* gene, which links cytoskeletal actin filaments to membrane proteins. The dystrophin protein acts as a shock absorber during muscle fiber contraction by linking the actin of the contractile apparatus to the layer of connective tissue that surrounds each muscle fiber (Koenig et al., 1988; Fairclough et al., 2013; Aartsma-Rus et al., 2016).

Due to the lack of dystrophin, the connection between the actin cytoskeleton and connective tissue is lost, inducing excessive membrane fragility and permeability, dysregulation of calcium homeostasis, and oxidative damage, which results in muscle cell necrosis and a chronic inflammatory state. Initially, muscle necrosis is followed by regeneration, but with age, the regenerative ability of myofibers is lost and muscle fibers are gradually replaced by connective and adipose tissue. It has been postulated that chronic injury and regeneration induce satellite cell exhaustion. Recent studies suggest that the absence of dystrophin in satellite cells impairs their ability to divide properly, thus reducing the generation of myogenic progenitors that are needed for proper muscle regeneration (Dumont et al., 2015). As a consequence, muscle function is lost (Muntoni et al., 2003; Deconinck and Dan, 2007; Falzarano et al., 2015).

DMD symptoms begin in early childhood, with degeneration occurring progressively in the skeletal musculature and ultimately in the heart and respiratory muscles, resulting in premature death (Hendriksen et al., 2015). Progressive weakness and muscle atrophy caused by degenerating muscle fibers begins in the lower extremities and pelvis before spreading into the upper extremities. Other symptoms include loss of some reflexes, a waddling gait, frequent falls, difficulty when rising from a sitting or lying position or when climbing stairs, changes to overall posture, and impaired breathing. Many children precipitously lose the ability to run or jump. The atrophied muscles, in particular the calf muscles, and less commonly, muscles in the buttocks, shoulders, and arms, may be enlarged by an accumulation of fat and connective tissue, causing them to look larger and healthier than they actually are ("pseudohypertrophy"). Bone thinning and scoliosis are common. Ultimately, a wheelchair becomes necessary, in most cases between 12 to15 years of age (Henricson et al., 2013).

As the disease progresses, the muscles in the diaphragm that assist in breathing and coughing become weaker. Affected individuals experience breathing difficulties, respiratory infections, and swallowing problems. Almost all DMD patients will develop cardiomyopathy (Aartsma-Rus et al., 2016). Pneumonia, compounded by cardiac involvement, is the most frequent cause of death, which typically occurs in the late teens or early 20s. However, improvements in multidisciplinary care, in particular respiratory care and various forms of assisted ventilation, have extended the life expectancy; numerous individuals with DMD now survive into their 30s, and some even into their 40s (Emery, 2002; Bushby et al., 2010; Bushby et al., 2010).

No pharmacologic or biological therapies proven to stop or reverse the progression of DMD have been approved in the US. Disease management consists primarily of preventive measures as well as active interventions to address the primary and secondary aspects of the disorder.

Page 22 of 75 Capricor, Inc. - Company Confidential

## 5.4. Risks and Benefits

In over 131 subjects treated with CAP-1002, the combination a favorable safety profile and preliminary indications of efficacy suggest a favorable risk-benefit profile of CAP-1002.

Based on these data, the benefit-risk balance for CAP-1002 is considered favorable, and warrants additional clinical investigation.

# 5.5. Trial Rationale

The proposed open label extension (OLE) trial will enroll subjects randomized to the Usual Care Treatment Group in the HOPE-Duchenne trial (CAP-1002-DMD-01) and who completed the 12-month follow-up period. All subjects enrolled in the OLE will receive CAP-1002.

CAP-1002 is intended to be used as a therapy to improve the morbidities associated with DMD and thus improve or prevent decline in muscle function through its composite immunemodulatory, anti-fibrotic, and regenerative mechanisms of action.

## 5.6. Dose Justification

#### 5.6.1. Dosing Interval

Data from HOPE-Duchenne show a maintenance of benefit in PUL with CAP-1002 treatment up to 3 months post dose that then wanes by 6 months. This observation that some benefits of a CAP-1002 dose may be transient inspired the plan for a repeat administration regimen in the proposed clinical trial, with a second dose administered after 3 months.

. Following a waning of the effect on cardiac function, repeat dosing of CDCs at an interval of 3 months led to a second improvement in cardiac function. However, repeat dosing of CDCs at an interval of 3 weeks, did not noticeably enhance exercise capacity or skeletal muscle force production beyond the effect achieved with one dose, which may be attributable in part to the abbreviated dosing interval.

#### 5.6.2. Dose Selection

The dose selected for testing in the open label extension trial was chosen because the dose already demonstrated preliminary efficacy via intracoronary infusion in the HOPE-Duchenne trial, and would be expected to be similarly efficacious via intravenous administration given what is known about cell biodistribution and engraftment post infusion by either route.

#### 5.6.3. Repeat Administrations

The other element of safety relevant for the open label extension trial and related to the planned dosing regimen, is the potential for an immune response to the allogeneic product, planned for repeated administrations. Several lines of evidence suggest that repeat administration of CAP-1002 should have low immunotoxicity risk in humans.

In fact, equivalent

primary (i.e., after a first dose) and secondary (i.e. after a second dose) efficacy benefits (i.e., improvements in LVEF) were observed using allogeneic and syngeneic CDCs in this study. Furthermore, there was no evidence of an increased cellular or humoral immune memory response using allogenic compared to syngeneic CDCs. These collective data suggest that repeat administration of CAP-1002 should be reasonably safe in humans.

# 5.7. Trial Population

The target population for this trial is pediatric and adult males with a diagnosis of DMD who were randomized to the Usual Care Treatment Group of the HOPE-Duchenne trial and completed the 12-month follow-up period, and meet the OLE trial eligibility criteria (see Section 8) that focus on minimizing risk of participation in the extension trial.

## 6. TRIAL OBJECTIVES AND PURPOSE

## 6.1. **Primary Objective**

The primary objective of this trial is to provide CAP-1002 to subjects who were randomized to the Usual Care Treatment Group of the HOPE-Duchenne trial and completed the 12-month follow-up period.

## 6.2. Secondary Objectives

The secondary objectives of this trial are to explore the safety and efficacy of intravenous administration of CAP-1002 with repeat dosing at Month 3.

# 7. INVESTIGATIONAL PLAN

## 7.1. Overall Trial Design

This Phase 2, multi-center, open label extension trial will provide CAP-1002 to subjects who were randomized to the Usual Care Treatment Group and completed 12 months of follow-up in the HOPE-Duchenne trial. The trial will assess the safety of CAP-1002, administered as two IV infusions, each separated by 3 months. All subjects will undergo targeted tests and procedures within 30 days prior to first infusion, unless otherwise stated, to confirm eligibility based on protocol inclusion and exclusion criteria.

Eligible subjects will undergo baseline safety and efficacy assessments (Table 3) prior to the first infusion of CAP-1002. Administration of CAP-1002 (Day 1) should occur within a maximum of 14 days following confirmation of eligibility; if a delay of more than 14 days between enrollment and CAP-1002 administration is unavoidable, a conversation between the Investigator and Medical Monitor should occur to determine the need for repeat assessments prior to infusion. For the purposes of this trial, enrollment is defined as the time consent is signed.

All intravenous infusions will be conducted in an outpatient setting at the investigative site on Day 1 and at Month 3. Subjects will be observed in the outpatient setting for at least two hours post infusion and then discharged the same day if medically cleared by the site Investigator.

A safety phone call will be performed 14 days ( $\pm 3$  days) after each CAP-1002 infusion, and if clinically indicated, an unscheduled in-person visit will be performed at the investigative site with targeted assessments based on presentation of signs and symptoms.

Blood samples will be collected at Week 4 and Month 4 ( $\pm$ 7 days, respectively) for DSA testing and safety laboratory assessments. Collection will occur either at the investigative site or remotely at a designated central laboratory patient service center.

Subsequent trial visits at the investigative site will occur at Months 3 and 6 ( $\pm$ 14 days, respectively). Subjects will complete safety and efficacy assessments at each of these visits and prior to CAP-1002 administration in the case of the Month 3 trial visit.

## 7.2. Trial Endpoints

### 7.2.1. Safety Endpoints

The *primary safety endpoints* include the incidence of the following from baseline through the 6-month timepoint:

- Acute respiratory decompensation within 2 hours following IP administration
- Hypersensitivity reaction
  - Hypersensitivity reaction is defined as a clinical syndrome including, but not limited to, fever, leukocytosis, or rash with onset  $\leq 2$  hours post infusion and lasting < 24 hours, in the absence of clinical signs of concomitant infection.
- All-cause mortality
- Serious adverse events

- Treatment-emergent adverse events related to IP or administration procedure
- Immune sensitization syndrome
  - Immune sensitization syndrome shall be defined as: (a) clinical signs and symptoms consistent with systemic inflammation (e.g., fever, leukocytosis, rash, or arthralgia) with onset  $\geq 24$  hours post infusion and the absence of clinical signs of concomitant infection, AND (b) elevation of anti-human leukocyte antigen (HLA) antibodies against the donor cells (i.e., DSAs), detected  $\leq 30$  days following onset of syndrome, of (i)  $\geq 2000$  mean fluorescent intensity (MFI) if baseline MFI  $\leq 1000$ , or (ii)  $\geq 2$  times baseline otherwise

#### 7.2.2. Exploratory Endpoints

The *exploratory endpoints* include the change from baseline to each assessment timepoint for the following assessments:

- All subjects
  - Mid-level (elbow) dimension of the PUL 1.2
  - Mid- and distal-level (elbow) dimension of the PUL 1.2
  - High-level (shoulder) dimension of the PUL 1.2
  - Left ventricular structure and function as assessed by cardiac MRI including regional systolic left ventricular wall thickening, ejection fraction, end-diastolic volume, end-systolic volume, stroke volume, regional wall thickness, and circumferential strain
  - Slow vital capacity (SVC), forced expiratory volume in one second (FEV1), forced vital capacity (FVC), peak expiratory flow (PEF), maximum inspiratory pressure (MIP), maximum expiratory pressure (MEP), peak cough flow (PCF), and inspiratory flow reserve (IFR)
- Ambulatory subjects only
  - 6-Minute Walk Test (6MWT)

## 7.3. Number of Subjects

Up to 10 subjects will be enrolled.

## 7.4. Treatment Assignment

All subjects will receive open-label CAP-1002 ( at Day 1 and infusion.

at Day 1 and Month 3 via IV

## 7.5. Dose Adjustment Criteria

There are no planned dose adjustments. Should an acute toxicity arise during the infusion (e.g., hypersensitivity reaction, pulmonary decompensation, etc.), the infusion should be terminated immediately, and the actual total dose administered recorded. Any decision about re-challenging

in a subsequent infusion should be made after discussions with the Investigator, Medical Monitor, Data Safety Monitoring Board (DSMB), and other medical experts that may be required to make an informed decision.

### 7.6. Criteria for Trial Termination

The trial may be terminated at any time and for any reason, including, but not limited to, a recommendation by the DSMB for safety reasons, an action by the FDA, or decision by Capricor.

Protocol No. CAP-1002-DMD-03 Amendment 1.0

#### Figure 1: Trial Design

Safety Outcome Measures: AEs, PE, VS, WT & HT, ECG, CBC w/ diff, Hgb, HCT & plts, basic metabolic panel, comprehensive hepatic panel, CK, CK-MB, cTnl, DSA Efficacy Outcome Measures: cMRI, PUL 1.2, 6MWT, core lab standardized PFTs (SVC, spirometry, MIP & MEP, PCF and IFR)

> Page 32 of 75 Capricor, Inc. - Company Confidential

#### Table 3: Schedule of Assessments

Procedure / Event 	Screening	Day 1 (Infusion #1)	Post-Infusion #1 Safety Monitoring	Week 4	Month 3 (Infusion #2)	Post-Infusion #2 Safety Monitoring	Month 4	Month 6 / Early Termination 
Trial Day (Visit Window)	≤30 days prior to Day 1		14 days (±3) after Infusion #1	30 days (± 7)	90 days (±14)	14 days (±3) after Infusion #2	120 days (± 7)	180 (±14)
Informed Consent / Assent	х							
Eligibility Assessment	Х	Х						
Prior & Concomitant Meds	х	Х	х		х	х		Х
Medical History	Х							
Medical Status Questionnaire		х			х			х
Adverse Events	Х	Х	Х		Х	х		х
CAP-1002 IV Infusion 		Х			Х			
Post-Infusion Safety Call 4			Х			х		
Vital Signs		Х			Х			Х
Height / Ulna Length 		Х			Х			х
Weight		Х			Х			Х
Physical Examination		Х			Х			х
12-Lead ECG		Х			Х			х
Serum Chemistry 	Х	Х		Х	Х		Х	х
Hematology 		Х		Х	Х		Х	Х
Cardiac Enzymes 		Х			Х			Х
HLA Typing 		Х						

Protocol No. CAP-1002-DMD-03 Amendment 1.0

Procedure / Event 	Screening	Day 1 (Infusion #1)	Post-Infusion #1 Safety Monitoring	Week 4	Month 3 (Infusion #2)	Post-Infusion #2 Safety Monitoring	Month 4	Month 6 / Early Termination 
Trial Day (Visit Window)	≤30 days prior to Day 1		14 days (±3) after Infusion #1	30 days (± 7)	90 days (±14)	14 days (±3) after Infusion #2	120 days (± 7)	180 (±14)
Donor-Specific Antibodies 		х		Х	х		х	Х
PUL 1.2		Х			Х			Х
6-Minute Walk Test 		Х			Х			х
Pulmonary Function Testing 		х			х			Х
Cardiac MRI 	х							Х

 Sites will complete assessments in the following sequence: 1) safety and other trial assessments, excluding blood collection (e.g., vital signs, height, weight, 12-lead electrocardiogram [ECG], etc.), 2) pulmonary function testing (PFT), 4) PUL 1.2, 5) 6MWT, 6) blood collection, 7) cardiac MRI (if applicable), and 8) CAP-1002 Infusion (if applicable). All efforts must be made for the same clinical evaluator to complete assessments for the same subject at the same time of day throughout the trial (preferably in the morning).

 All attempts must be made to perform the trial assessments indicated for the Month 6 visit (i.e., final comprehensive visit) for subjects that decide to early terminate early from the trial after starting at least one CAP-1002 infusion.

 All CAP-1002 infusions will be conducted in an outpatient setting at the investigative site. Subjects will be observed for at least 2 hours post infusion, including pulse oximetry monitoring for at least 30 minutes post infusion. Sites will observe local institutional policies related to parenteral infusions and post infusion monitoring.

 A safety phone call will be performed 14 days (±3 days) after each CAP-1002 infusion, and if clinically indicated, an unscheduled in-person visit will be performed at the investigative site with targeted assessments based on presentation of signs and symptoms.

 If standing height cannot be measured, height will be calculated using a measurement of ulna length per Section 13.1.2.

 Blood samples will be collected using trial-specific laboratory kits, and then shipped to and tested at a central laboratory. Required sample collection for a visit may occur on multiple days; if the visit includes a CAP-1002 infusion, sample collections should occur prior to CAP-1002 administration.

 Basic metabolic panel (Glucose, Sodium, Potassium, Chloride, Bicarbonate, BUN, Creatinine, Calcium), comprehensive hepatic panel (Albumin, Alkaline Phosphatase, Total Protein, ALT, AST, Direct Bilirubin, Total Bilirubin)

 CBC with WBC differential, hemoglobin, hematocrit and platelet count

 CK-MB and troponin I

Ambulatory subjects

PFT testing sequence: SVC, forced maneuver (FEV1/FVC/PEF), MIP, MEP, PCF, and IFR.

Protocol No. CAP-1002-DMD-03 Amendment 1.0

Subjects will undergo cardiac MRI if they are physically capable as determined by an Investigator. Subjects that cannot complete a cardiac MRI as part of the trial will complete an echocardiogram at screening using the site's local equipment, acquisition protocol, and evaluation procedures. The reported LVEF from a local interpretation, whether it's measured via cardiac MRI or echocardiogram, will be used to assess eligibility (exclusion criterion 1).

## 8. SELECTION AND WITHDRAWAL OF SUBJECTS

Subjects who meet all inclusion criteria and no exclusion criteria will be eligible for the trial.

## 8.1. Subject Inclusion Criteria

Inclusion criteria will be assessed within 30 days prior to first infusion on Day 1 unless otherwise noted:

- 1. Documented enrollment in the Usual Care Treatment Group of the HOPE-Duchenne trial and completion of trial follow-up through Month 12.
- 2. Willing and able to provide informed consent to participate in the trial if  $\geq 18$  years of age, and assent with parental or guardian informed consent if < 18 years of age
- 3. Adequate venous access for intravenous CAP-1002 infusions and routine blood collections in the judgement of the Investigator
- 4. Assessed by the Investigator as willing and able to comply with the requirements of the trial

# 8.2. Subject Exclusion Criteria

Exclusion criteria will be assessed within 30 days prior to first infusion on Day 1 unless otherwise indicated:

- 1. Left ventricular ejection fraction (LVEF) < 35% within 6 months of screening
- 2. Planned or likely major surgery in the next 6 months after planned first infusion
- Risk of near-term respiratory decompensation in the judgment of the investigator, *or* the need for initiation of non-invasive ventilator support as defined by serum bicarbonate ≥ 29 mmol/L at screening
- 4. History of non DMD-related chronic respiratory disease including, but not limited to, asthma, bronchitis, and tuberculosis
- 5. Acute respiratory illness within 30 days prior to screening
- 6. Known hypersensitivity to dimethyl sulfoxide (DMSO) or bovine products
- 7. Treatment with investigational product  $\leq 6$  months prior to first infusion
- 8. History, or current use, of drugs or alcohol that could impair their ability to comply with participation in the trial
- 9. Inability to comply with the investigational plan and follow-up visit schedule for any reason, in the judgment of the investigator

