#### **Objectives**:

*Primary*: To provide CAP-1002 to subjects who were randomized to the Usual Care Treatment Group of the HOPE-Duchenne trial and completed 12 months of follow-up.

*Secondary*: To explore the safety and efficacy of intravenous administration of CAP-1002 with repeat dose at Month 3.

**Methodology:** This Phase 2, multi-center, open label extension trial will provide CAP-1002 to subjects that were randomized to the Usual Care Treatment Group of the HOPE-Duchenne trial (CAP-1002-DMD-01) and explore the safety of two intravenous administrations of CAP-1002, each separated by three months. Subjects will undergo targeted tests and procedures during a 30-day screening period to determine eligibility based on protocol inclusion and exclusion criteria.

Eligible subjects will undergo baseline safety and efficacy assessments on Day 1 prior to their first infusion of CAP-1002. Administration of CAP-1002 (Day 1) should occur within a maximum of 14 days following confirmation of eligibility; if a delay of more than 14 days between enrollment and IP administration is unavoidable, a conversation between the Investigator and Medical Monitor should occur to determine the need for repeat assessments prior to infusion.

All CAP-1002 infusions will be conducted in an outpatient setting at the investigative site on Day 1 and Month 3. Subjects will be observed in the outpatient setting for at least two hours post infusion and then discharged the same day if medically cleared by the site Investigator.

A safety phone call will be performed 14 days ( $\pm 3$  days) after each CAP-1002 infusion, and if clinically indicated, an unscheduled in-person visit will be performed at the investigative site with targeted assessments based on presentation of signs and symptoms.

Blood samples will be collected before each CAP-1002 administration (Day 1 and Month 3), after each CAP-1002 infusion (Week 4 and Month 4) and at Month 6, unless otherwise indicated, for donor specific antibody (DSA) testing and routine serum chemistries, hematology and cardiac enzymes. HLA

typing will occur before the first CAP-1002 administration on Day 1. Collection will occur either at the investigative site or remotely at a designated central laboratory patient service center.

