# 8.4. Subject Withdrawal Criteria

Every effort will be made to have each subject complete all elements of the trial. If a subject has started at least one IP infusion and withdraws prior to trial completion, all attempts must be made to perform the trial assessments indicated for the Month 6 visit (i.e., final comprehensive visit).

Criteria for withdrawal from trial participation include the following reasons:

- A subject may withdraw his consent at any time without prejudice to his care.
- At the discretion of the Investigator, the subject may be withdrawn from the trial for lack of adherence to the investigational plan.
- A subject may be withdrawn from the trial for an acute reaction to CAP-1002 or other safety issue that prevents repeat infusions. In this instance, the subject should be followed on trial for at least 3 months after the last CAP-1002 infusion and then complete a final comprehensive visit.

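### The bicarbonate limit gates Infusion 1 only, so Infusion 2 can be given before the Month 3 result is known; infusion-linked events are also not reported by infusion

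*Protocol*

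**What the plan says.** **Before Infusion 1.** Protocol Section 8.2 opens with "Exclusion criteria will be assessed within 30 days prior to first infusion on Day 1 unless otherwise indicated". Exclusion 3 has two limbs: the investigator's judgment of near-term decompensation risk, and "the need for initiation of non-invasive ventilator support as defined by serum bicarbonate" of 29 mmol/L or more at screening. Table 3 allows screening up to 30 days before Day 1 and marks Eligibility Assessment at Screening and Day 1 only; SAP Appendix B shows the same. Under Section 7.1, if more than 14 days must pass between enrollment and infusion, "a conversation between the Investigator and Medical Monitor should occur to determine the need for repeat assessments prior to infusion".

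**At Infusion 2.** Chemistry, which includes bicarbonate, is scheduled at Month 3. Table 3 footnote 1 ends its sequence with "6) blood collection, 7) cardiac MRI (if applicable), and 8) CAP-1002 Infusion (if applicable". Footnote 6 says samples are shipped to and tested at a central laboratory, may be taken over several days, and "if the visit includes a CAP-1002 infusion, sample collections should occur prior to CAP-1002 administration". Section 10.6 requires the other assessments to be completed before infusion. It does not mention results.

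**Ways to stop or delay Infusion 2.** After toxicity during an infusion, a decision on re-challenge "in a subsequent infusion should be made after discussions with the Investigator, Medical Monitor, Data Safety Monitoring Board (DSMB), and other medical experts" (Section 7.5). Section 8.4 adds: "A subject may be withdrawn from the trial for an acute reaction to CAP-1002 or other safety issue that prevents repeat infusions". Neither contains a respiratory or laboratory threshold.

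**Analysis.** SAP Section 7 promises an overall table of the primary safety endpoints. Section 7.1 lists and summarises adverse events within 24 hours of administration, and counts a subject with the same event once while also giving event counts. No split by infusion is stated. Section 5.12 already summarises administration by visit.

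**The concern.** Acute respiratory decompensation within 2 hours of dosing is a primary safety endpoint, and the protocol's background describes breathing muscles weakening as the disease progresses. The plan sets one objective respiratory laboratory limit before the first exposure. It draws the same test before the second exposure but does not require anyone to look at it. A subject whose bicarbonate has passed 29 mmol/L since Week 4 could be infused without the Investigator knowing.

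The second part concerns what the trial can report. The secondary objective is safety and efficacy with a repeat dose at Month 3. If infusion-linked reactions are pooled over both doses, the tables do not show whether the second dose behaved differently from the first.

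**Working it through.** **1. Is there a rule for Infusion 2 in the readable text?**

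| Item | Infusion 1 | Infusion 2 |
|---|---|---|
| Eligibility Assessment (Table 3) | Screening and Day 1 | Not marked |
| Bicarbonate limit of 29 mmol/L (8.2) | At screening | None stated |
| Same-day chemistry (Table 3) | Collected before infusion | Collected before infusion |
| Same-day result needed (footnote 6, 10.6) | Not stated | Not stated |
| Donor-specific antibody as a gate (10.2) | No, given regardless of level | No |
| Age limit on the qualifying bicarbonate | 30 days | None stated |

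Sections 7.6 (trial termination) and 17.5 (action after deviations) also allow stopping, but set no respiratory or laboratory criterion.

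**2. How old is the latest bicarbonate if the Month 3 result is not awaited?** The plan states no figure to reproduce. Inputs from Table 3:

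- Week 4 draw: 30 ± 7, so Day 23 to 37.
- Infusion 2: 90 ± 14, so Day 76 to 104.

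Age at infusion = day of Infusion 2 minus day of the Week 4 draw:

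- Shortest: 76 − 37 = 39 days.
- Nominal: 90 − 30 = 60 days.
- Longest: 104 − 23 = 81 days.

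Against the 30-day limit these are 39/30 = 1.3, 60/30 = 2.0 and 81/30 = 2.7 times as old. Since 39 exceeds 30, the Week 4 value can never meet the limit used before Infusion 1, so a later draw is needed.

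**3. What does deferral do to later visits?** From nominal Day 90, the window leaves 104 − 90 = 14 days. If Infusion 2 moves to Day 104:

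- The Month 4 draw (120 ± 7, Day 113 to 127) falls 113 − 104 = 9 to 127 − 104 = 23 days after it. Week 4 falls 22 to 36 days after Day 1.
- Timed at 30 ± 7 days after the actual Infusion 2, Month 4 becomes Day 127 to 141.
- Month 6 (180 ± 14, Day 166 to 194) falls 166 − 104 = 62 to 194 − 104 = 90 days after it.

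**4. What does pooling hide?** This is an illustration, not a forecast. Suppose all 10 subjects receive both infusions and 3 react at one infusion only. The pooled table reads 3/10 whichever infusion it was. By infusion it reads 0/10 then 3/10, or the reverse. Exact (Clopper-Pearson) 95% intervals:

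- 0/10: upper limit 1 − 0.025^(1/10) = 30.8%, so 0 to 30.8%.
- 3/10: the 2.5% point of Beta(3, 8) and the 97.5% point of Beta(4, 7), so 6.7% to 65.2%.

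A subject who reacts in the same way at both infusions shows as one subject with two events.

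**The case against.** The case on the other side has several sound parts.

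- **Exclusion 3 selects entrants.** It is not written as a retreatment rule, and no document says that CAP-1002 should be withheld above 29 mmol/L or that bicarbonate predicts decompensation within 2 hours. This stands and limits the claim to consistency between the two doses.
- **Day 1 follows the same pattern.** Its chemistry is also shipped, and no readable text requires that result before infusing. Infusion 1 can rest on a screening value up to 30 days old. This stands too, so the fair standard for Infusion 2 is 30 days and nothing stricter.
- **The 14-day trigger is only a conversation.** A reader might take it as a limit on how long a result is valid. Section 7.1 does not say that.
- **Month 3 checks are objective.** Pulmonary function is measured on site before infusion and can show decline short of overt illness. SpO2, physical examination, adverse event review and the ventilatory-support question are also scheduled. Section 16.2 has monitors verify documented investigator oversight of abnormal laboratory values, so a raised Week 4 value should be noticed. These are real safeguards, but none has a threshold and none reveals a result still in transit.
- **The text is incomplete.** Parts of Section 10 are not readable here, and the Investigational Product Manual and Manual of Procedures are not available. A pre-infusion rule could sit there.
- **The SAP point is small.** With 10 subjects or fewer, the listings allow each event to be traced to an infusion by hand.

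**Conclusion.** The point holds in limited form. In the readable text, the bicarbonate limit gates Infusion 1 only. Infusion 2 can proceed on Investigator judgment with the Month 3 value drawn but unreported, and the last scheduled value is then 39 to 81 days old. This affects up to 10 infusions. It is worth correcting because the test is already scheduled and the change is cheap.

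Two stronger readings are tempting. One is that the plan exposes subjects to a demonstrated respiratory hazard at the second dose. The documents give no rate of raised bicarbonate, no rate of decompensation and no link between the two, so no harm is quantified or claimed. The other is that nothing guards Infusion 2. The Month 3 assessments and Sections 7.5 and 8.4 show otherwise; what is missing is a stated criterion and a reviewed result.

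The SAP gap is one of presentation, with a modest gain from closing it. The verdict assumes that the unreadable parts of Section 10 and the two manuals hold no such rule. If they do, a cross-reference is enough.

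**What to change.** **Protocol, Table 3 footnote 6 and Section 7.5.** Require the Investigator to review a bicarbonate result no more than 30 days old, together with the same-visit pulmonary function tests and SpO2, before Infusion 2. Draw the Month 3 chemistry early under the multi-day collection that footnote 6 already allows. For an infusion on Day 76 any earlier draw falls before the visit window opens, so state that it still counts as the Month 3 sample. The Synopsis already covers Month 3 when it says "Collection will occur either at the investigative site or remotely at a designated central laboratory patient service center". Section 7.1 gives that option only for Week 4 and Month 4, so align it.

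If bicarbonate is 29 mmol/L or more, or there is near-term decompensation risk or an acute respiratory illness, the Investigator and Medical Monitor should confer before infusing. Deferral within Day 76 to 104 is an option, and withdrawal is not automatic. This keeps the primary objective of providing CAP-1002.

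*Cost:* a short amendment and possibly one extra blood-draw trip per subject. If Infusion 2 is deferred, time the Month 4 draw from the actual infusion and book Month 6 late in its window.

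**SAP Sections 7 and 7.1.** Show adverse events within 24 hours, acute respiratory decompensation and hypersensitivity by infusion number (1 or 2), with the number infused at each as denominator.

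*Cost:* one added column in a few tables.
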